## 11.4.2 Primary Safety Analysis

The primary safety variable is all-cause mortality or unplanned cardiovascular hospitalizations as days lost due to unplanned cardiovascular hospitalizations or death.

The number of days lost due to death of any cause or unplanned cardiovascular hospitalizations will be analysed by a Wilcoxon signed-rank test comparing both treatment groups. Additionally, the number of days lost due to death of any cause or unplanned cardiovascular hospitalizations will be analysed descriptively by treatment group and in total.

## 11.4.3 Secondary Efficacy Analyses

### 11.4.3.1 Adherence to medication

The primary efficacy analyses will also be repeated for each drug class (ACEi/ARB, BB, MRA). The percentage of patients with a mean PDC  $\geq 80\%$  (=adherent), and percentage of patients with a PDC  $\geq 80\%$  for each drug class (sensitivity analyses for a cutpoint  $\geq 88\%$ ) will be calculated.

### 11.4.3.2 Quality of life (Minnesota Living with Heart Failure Questionnaire, total score)

The changes to baseline of the total score of the Minnesota Living with Heart Failure Questionnaire after 1 year and, if sufficient data are available, after 2 years will be analysed by an ANCOVA, including treatment as fixed effect and total score at baseline as covariate. Parameter estimates and adjusted mean differences will be shown together with their corresponding p-values and 95% confidence intervals.

Additionally, the total score as well as the corresponding change to baseline will be analysed descriptively by visit, treatment group and in total.

### 11.4.3.3 Patient global assessment (PGA)

The self-reported patient global assessment (PGA) will be displayed by numbers and percentages by visit (after 1 year and, if sufficient data are available, after 2 years), treatment group and in total. A Chi-Square test for treatment comparison will be used.

### 11.4.3.4 PHQ-9

The PHQ-9 total score and the changes to baseline will be analysed descriptively by visit (after 1 year and, if sufficient data are available, after 2 years) for each treatment group and in total. t-tests for comparing treatment groups will be performed.

### 11.4.3.5 Self estimated adherence

Self-estimated adherence will be analysed descriptively by visit (after 1 year and, if sufficient data are available, after 2 years), for each treatment group and in total. T-tests for comparing treatment groups will be performed.

## 11.4.4 Secondary Safety Analyses

The following secondary safety variables will be analysed by descriptive methods and exploratory p-values:

- All-cause mortality or unplanned cardiovascular hospitalizations as recurrent event (number)
- Unplanned cardiovascular hospitalizations (recurrent event, number)
- Unplanned hospitalizations for heart failure (recurrent event, number)
- Days lost due to hospitalizations of any cause or death
- Unplanned all-cause hospitalizations
- All-cause mortality

All primary and secondary variables are also analysed for the PP Population. These analyses are only considered as exploratory.

### 11.4.5 Subgroup Analyses

Several pre-specified subgroups will be explored.

The following subgroups are planned:

- Minimization-criteria:
  - Sex (male/female)
  - Age (<75, ≥75 years)
  - NYHA functional class (I and II, III and IV)
  - PHQ-9 (depression score <10, ≥10)
  - Diabetes mellitus (yes/no)
  - The study region will be omitted since this may lead to an over determination of the analysis model.
- Time between last heart failure hospitalization and randomization (≤ 3 months vs. > 3 months before study)
- Number of different drug substances (median at randomization), as an indicator of the level of illness burden
- Number of different co-morbidities (median at randomization), as a further indicator of the level of illness burden
- Heart failure medication at baseline (BB versus BB plus ACEi/ARB, BB plus ACEi/ARB versus BB plus ACEi/ARB/MRA) (subpopulations)
- Heart rate at baseline (≤ 75 vs. > 75 min)
- QoL score (MLHFQ Median)
- HFrEF vs. HFmrEF/HFpEF (LVEF <40% vs. ≥ 40%)

Each subgroup and the corresponding interaction with treatment group will be included into the analysis model (the PDC of each drug class will be analysed by an ANOVA, for the mean PDC ≥80% a logistic regression model will be used).

### 11.4.6 Randomization

Eligible patients are assigned in a 1:1 ratio to the intervention or control group. Minimization with 20% residual randomness is used to ensure balance of the following characteristics: Gender (male/female), age (<75, ≥75), NYHA functional class (I and II, III and IV), PHQ-9 (score <10, ≥10), diabetes mellitus (yes/no), study region (according to regional Associations of Statutory Health Insurance Physicians (KV-Region)).

A web-based randomization tool developed by IZKS Mainz is used within this study allowing investigators to randomize patients via a secure web interface.

Subjects withdrawn from the study retain their identification codes (i.e. patient number). New subjects must always be allotted a new identification code.

### 11.4.7 Blinding

PHARM-CHF is a prospective multicentre, randomized controlled study. Patients are randomized by the recruiting physician on an individual level. Pharmacists are unaware of the control patients. All other investigators, committees, and staff remain fully blinded throughout the study to the randomization status of the patients.

## 11.5 Methods to Avoid Bias

### 11.5.1 Selection Bias

See randomization.

### 11.5.2 Performance Bias

Potential bias:

Physicians (unblinded) treat patients of the intervention group differently than patients of the control group to reach the aim of the study.

→ Difficult to avoid, the design of the study seems necessary for a realistic study setting. However, the interdisciplinary approach to improve medication adherence is part of the study design. In addition, the CHF medication in both groups will be analysed at V1 and V5.

Contamination at medical practices: physicians intensively engage with the topic (i.e. heart failure, medication adherence and drug-related problems) and apply this additional knowledge to the control patients.

→ Difficult to avoid, the design seems necessary for a realistic study setting. Pharmacists are unaware of the control patients.

Higher detection rate of potential events: Patients in the intervention group receive a more intensive care and have a more intensive contact with health care professionals. The intensified contact could lead to a higher detection rate of events. There is a risk that the recording rate of events differs between control and intervention group.

→ Involvement of e.g. health insurance companies to collect events recorded in the health insurance files.

### 11.5.3 Exclusion Bias

Potential bias:

Patients of the intervention group may stop following the study protocol because they do not want to visit the pharmacy as frequent as required or because they do not like the weekly dosing aids.

→ Intention-to-treat-analysis

## 12 Adverse Events

Due to the fact that no investigational medical drug or device is tested, the standard of care is not altered during the study and hard endpoints for this study are chosen (mortality or unplanned hospitalization). Therefore, only hospitalizations and mortality will be documented.

## 13 Ethical and Legal Aspects

The procedures set out in this study protocol, pertaining to the conduct, evaluation, and documentation of this study, are designed to ensure that all persons involved in the study abide by Good Clinical Practice (GCP) so far applicable and the ethical principles described in the current revision of the Declaration of Helsinki. The study is carried out according to the legal and ethical requirements (e.g. data protections laws). Written informed consent is obtained from all patients.

### **13.1 Responsibilities of Scientific Heads**

The scientific heads ensure that all persons assisting with the study are adequately informed about the protocol, any amendments to the protocol, the study procedures, and their study-related duties and functions. They maintain a list of all qualified persons to whom they have delegated significant study-related duties.

### **13.2 Approval of Study Protocol and Amendments**

Before the start of the study, the study protocol, informed consent document, and any other appropriate document are submitted to the independent Ethics Committees (EC). Before the first subject is enrolled in the study, all ethical and legal requirements must be met.

### **13.3 Ongoing Information for Independent Ethics Committee**

The EC will be informed of all subsequent protocol amendments, which might require formal approval.

## **14 Committees**

Three different committees are involved in this study:

A Steering Committee (Executive Board) is in charge of strategic advice. Furthermore, a blinded clinical event committee (CEC) for adjudication of hospitalizations and a Committee for Data Protection (DPC) have been implemented. These committees follow a specified charter, which describes the working procedures.

## **15 Agreements**

### **15.1 Financing of the Study**

The study is financed by ABDA, and the pharmacists' state chambers or foundations of Bavaria (Lesmueller-Foundation), North Rhine, and Westphalia-Lippe as well as the Foundation Pharmaceutical Care (FI).

### **15.2 Reports**

ABDA prepares reports in collaboration with Leipzig University, PMV and IZKS Mainz.

### **15.3 Publication**

All information concerning the study is confidential before publication. However, the study protocol will be accessible on the homepage developed for the study ([www.pharm-chf.de](http://www.pharm-chf.de)) for authorized users. The study has been appropriately registered with Clinical Trials.gov Identifier: NCT01692119, before the first patient has been enrolled.

COPD Chronic Obstructive Pulmonary Disease	PHQ Patient Health Questionnaire
CV Cardiovascular	PKV Private Krankenversicherung (Private Health Insurance)
DDD Defined Daily Dose	PP Per Protocol
DMP Disease Management Program	PRIME-MD Primary Care Evaluation Of Mental Health Disorders
DRP Drug-Related Problems	PRN pro re nata
DSM-IV Diagnostic and Statistical Manual of Mental Disorders	QoL Quality of Life
eCRF Electronic Case Report Form	SAS Statistical Analysis Software
EF Ejection Fraction	SHI Statutory Health Insurance
GFR Glomerular Filtration Rate	SQL Structured Query Language
GKV Gesetzliche Krankenversicherung (Statutory health Insurance)	TIA Transient Ischemic Attack
GP General Practitioner	V Visit
HbA1c Hemoglobin A1c	WHO World Health Organization
HDL High Density Lipoproteins	
HFmrEF Heart Failure with Mid-range Ejection Fraction	
HFpEF Heart Failure with Preserved Ejection Fraction	
HFREF Heart Failure with Reduced Ejection Fraction	

List of Tables

Table 1 Visit schedule and data collection.....	8
Table 2 Violation of major entry criteria and intention-to-treat population.....	10
Table 3 Major protocol violation and per-protocol population	10
Table 4 PDC analyses - definition for 365 days' follow-up.....	17
Table 5 Secondary safety variables - Definition of patients' individual follow-up time	20

1 Background

Heart failure is one of the most prevalent diseases. In Germany, approximately 2.8 million patients suffer from heart failure. The prevalence increases with age and amounts to more than 10% in people aged 80 and older. In the elderly, heart failure is the most frequent cause for hospital admissions in Germany and the third most frequent cause of death. In 2008, the costs for treatment of patients with heart failure were estimated to 3.2 billion Euro. The continuous intake of several medicines is an essential part of the therapy. Several large clinical studies have reported that pharmacotherapy taken according to the guidelines, can increase quality of life, improve morbidity, and decrease mortality. However, in daily practice this effect can often not be achieved. Major reasons include medication non-adherence and other drug-related problems.

1.1 Objectives

The aim of PHARM-CHF is to investigate, whether a continuous interdisciplinary intervention improves medication adherence (primary efficacy variable of interest) and leads to a reduction of hospitalizations and mortality (primary safety variable of interest) in elderly patients with CHF.

The primary efficacy variable is medication adherence to cardiovascular medication, pre-specified as a significant difference of the proportion of days covered (PDC) between the intervention and control group within 365 days following randomization measured by pharmacy claims data.

The primary safety variable is days lost due to blindly adjudicated unplanned cardiovascular hospitalizations or death of any cause.

1.2 Sample size considerations

Assuming a baseline PDC for cardiovascular medication of 0.7 and a standard deviation of the PDC of 0.22 a sample size of N=176 (88/group) patients is needed to detect a 10% difference between the intervention group and the usual care group with a power of 85% and an alpha of 5%. Assuming a dropout and lost to follow-up of 30% N=248 patients have to be enrolled in the study. The planning is based on a two-sided t-test and performed by means of SAS Version 9.4.

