STUDY POPULATION	
Inclusion Criteria
 
 
- Age: 60 years and older
 
- Diagnosis of chronic heart failure (CHF)
 
- Stable CHF medication including a diuretic
 
- Hospitalization for decompensated heart failure within past 12 months OR a value of <math>\geq 350</math> pg/mL for BNP or <math>\geq 1400</math> pg/mL for NT-proBNP
 
- Written informed consent
 

	
Exclusion Criteria
 
 
- Regular/assisted use of a weekly dosing aid
 
- Unwillingness or inability to visit a participating pharmacy once a week
 
- Planned cardiac surgery
 
- Life-expectancy < 6 months
 
- Unwillingness or inability to comply with the study protocol (including drug abuse or alcohol dependency)
 
- Participation in other studies (currently or in the last 4 weeks)
 

DURATION OF THE STUDY	The mean follow-up is expected to 24 months with a minimum of 12 months.
NUMBER OF SUBJECTS	
N = 248
 
 
- Estimated effect of intervention: 10% (SD 22%)
 
- <math>\alpha = 0.05</math>, power: 85%
 
- Calculated sample size: 176 + 30% drop out
 

STUDY SITES	
Approximately 40 medical practices
 
Approximately 80 pharmacies

STUDY VISITS	
Intervention and control group:
 
 
- Visits in the medical practice at baseline (V1), after 12 months (V3), and at the end of the study (V6), and, if applicable, after 24 months (V5)
 
- Telephone visits by the medical practice after 6 months (V2) and, if applicable, after 18 months (V4)
 

INTERVENTION	
Regular, pharmacy based intervention conducted in cooperation with the treating physician:
 
 
- Medication review (Type 2a) at baseline: Recording of all medicines currently taken (prescribed medication and self-medication), check for drug-related problems, consolidation of a medication plan considering medication list of treating physician
 
- Regularly (weekly or bi-weekly): Dose-dispensing of the medication (weekly dosing aid), discussion and counselling regarding medication, adherence, potential side effects, and signs and symptoms of cardiac decompensation, blood pressure and pulse measurement, updating medication plan if necessary
 
- If required: Contact with patients' physician
 

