## 11 Biometrics

### 11.1 Sample Size

[figure not shown]

Figure 2: Sample Size Calculation

The primary efficacy variable is adherence to CHF medication. We conservatively assume an improvement of the summary PDC  $\geq 10\%$  in the intervention group compared to usual care as clinically relevant.

Assuming a mean PDC in the year before randomization of approximately 0.7 a sample size of  $N=176$  patients (88/group) is needed to detect a 10% (SD 22%) improvement between the intervention group and the usual care group with a power of 85% and an alpha of 5%. Assuming a dropout and lost to follow up of 30%  $N=248$  patients have to be enrolled in the study.

The study is powered for the primary efficacy variable only.

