7.8 Primary efficacy analysis

The primary efficacy analysis is the analysis of the PDC between baseline (day of randomization) and 365 days. The pharmacy claims data will be provided by data processing centres and health insurance funds. However, health insurance data were not available for all patients included in the study. Differences between patients with data from data processing centres and data from health insurance funds cannot be excluded. Therefore, an analysis will be performed comparing the data from health insurance funds and data processing centres. The analysis will be conducted twice. On the one hand, the analysis will be adjusted for data from health insurance funds (yes/no). And on the other hand, the analysis will be adjusted for data from health insurance funds (yes/no) and for baseline adherence (yes/no).

Analysis adjusted for data from health insurance funds only

The PDC (adjusted for data from health insurance funds only) will be analysed by a two-sided stratified Wilcoxon signed-rank test (van Elteren test) on a two-sided level of significance of 5%. The level of significance will not be divided among further hypotheses.

The following hypothesis will be tested:

$H_0: m_i = m_c$ vs. $H_1: m_i \neq m_c$,

Where m_i denotes the median value of the intervention group and m_c denotes the median value of the control group.

The following SAS code can be used:

```
proc freq data=xxx;  
    table updated*treatment group*PDC / cmh scores=modridit noprint;  
run;
```

Analysis adjusted for data from health insurance funds and baseline adherence

The PDC (adjusted for data from health insurance funds and baseline adherence) will be analysed by an analysis of covariance (ANCOVA). Treatment group will serve as a fixed effect and baseline adherence will serve as a random effect. Treatment groups will be compared on a two-sided level of significance of 5%. The level of significance will not be divided among further hypotheses.

The following hypothesis will be tested:

H0: $\mu_i = \mu_C$ vs. H1: $\mu_i \neq \mu_C$,

Where μ_i denotes the mean value of the intervention group and μ_C denotes the mean value of the control group.

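### Enrolling 248 with 30% dropout leaves 173.6 patients, slightly below the 176 the plan requires; the exact figure is 252, and the gap has no practical effect

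*SAP*

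**What the plan says.** SAP 1.2 assumes a baseline proportion of days covered (PDC) of 0.7 and a standard deviation of 0.22. It states that 176 patients (88 per group) are needed for 85% power at alpha 5%. It continues: "Assuming a dropout and lost to follow-up of 30% N=248 patients have to be enrolled in the study". It also names the planning method: "The planning is based on a two-sided t-test".

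Protocol 11.1 gives the same 176, 30% and 248. The Protocol synopsis shortens the step to "Calculated sample size: 176 + 30% drop out" under N = 248. Protocol 7.1.2 treats 248 as a minimum.

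The primary efficacy test in Protocol 11.4.1 and SAP 7.8 is the stratified van Elteren test. SAP 7.8 adds a second, baseline-adjusted primary analysis by ANCOVA on means. SAP Tables 2 and 3 report 258 randomised, 237 in the ITT population and 227 in the per-protocol population.

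**The concern.** A sample-size paragraph should close: the enrolled number, reduced by the stated loss, should return the evaluable number. Here it returns 173.6 where the same paragraph calls for 176. The synopsis does not help, because its shorthand read literally as 176 × 1.30 gives 228.8, which is not 248 either.

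What is at stake is reproducibility. These figures appear in three places, and someone who recomputes them from the stated inputs will not arrive at 248.

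**Working it through.** **Inputs.** Difference 0.10, SD 0.22, two-sided alpha 0.05, power 0.85, two-sided t-test, 30% dropout (SAP 1.2); 1:1 allocation (SAP 1.4).

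**1. Reproduce 176.** Exact (non-central t) power:
- 87 per group: 84.64%
- 88 per group: 85.05%

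So 88 per group is the smallest size that reaches 85%, and 176 reproduces. The 10% is therefore an absolute difference of 0.10. A relative 10% of 0.7 (0.07) would need 178 per group by the normal approximation.

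**2. Inflate for dropout.** N = n/(1 − d):
- 176/0.70 = 251.4, so 252 (126 per group)
- 248 × 0.70 = 173.6, which is 2.4 below 176
- 252 − 248 = 4 patients, or 4/252 = 1.6%

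**3. What 248 does correspond to.**
- Dropout implied by 248 and 176: 1 − 176/248 = 29.0%. Check: 176/0.71 = 247.9.
- Normal approximation: n per group = 2 × (1.960 + 1.036)² × (0.22/0.10)² = 2 × 8.976 × 4.84 = 86.9. The total is 173.8, and 173.8/0.70 = 248.3.

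The second line is a plausible origin, but no document states it.

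**4. Cost in power.** With 173.6 evaluable (86.8 per group), t-test power is 84.56%, against 85.05% at 88 per group. The difference is about 0.5 points.

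**5. What recruitment delivered.** The powers below use the planning values 0.10 and 0.22.

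| Set | Size | t-test power |
|---|---|---|
| 258 randomised, less 30% | 180.6 | 85.9% |
| ITT | 237 (110/127) | 93.5% |
| Per protocol | 227 (102/125) | 92.4% |

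Of the 258 randomised, 82 could be lost (82/258 = 31.8%) before the count fell below 176.

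**6. Rank-test power at 88 per group.** The documents do not give the PDC distribution or the share of patients with insurance-fund data, so these are assumptions.
- Normal PDC: 83.4% from the asymptotic efficiency of 0.955. A van Elteren simulation (4,000 runs, two strata, 50% or 80% with fund data) gave about 83%.
- Beta-distributed PDC with means 0.70 and 0.80 and SD 0.22: 96.0% to 96.5% in the same simulation. These two distributions differ in shape as well as location, which favours a rank test.
- Theoretical floor for a pure location shift (efficiency 0.864): 79.5%.

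**The case against.** The strongest reply is that 248 is not a mistake in method. It follows from a proper division by 0.70 if the normal-approximation size is used, and 176 is the exact t-test version of the same calculation. On that account two standard formulas were mixed and the discrepancy is rounding. The synopsis entry is a bullet-point shorthand, 248 is a minimum, and recruitment passed it. All of this stands as far as materiality goes. It does not make the printed text consistent, because 248 is placed beside 176 and not beside 174.

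A reader might infer that dropout was handled by multiplying by 1.30. It was not: that gives 229, a figure no document uses.

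A reader might also infer that the 85% is wrong because the primary test is rank-based. The documents do not support that. SAP 1.2 says openly that planning used a t-test, and SAP 7.8 includes an ANCOVA on means, for which a t-test is an ordinary planning basis. The Protocol's sample-size figure is not visible in the text reviewed, so nothing can be said about the method it names. The rank-test power may lie below or above 85%. The 83% needs normal PDC, yet a normal model with mean 0.80 and SD 0.22 puts about 18% of patients above 1.0, which PDC cannot exceed.

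**Conclusion.** The statement is wrong as written but minor. At the stated 30% loss, 248 enrolled patients do not yield 176; the exact figure is 252. The shortfall is 2.4 evaluable patients and about 0.5 points of t-test power, and this part is plain arithmetic on the stated inputs.

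It would be a mistake to infer that the trial fell short of its target or is underpowered. With 258 randomised, 180 remain even at 30% loss, and 237 are in the ITT population. One caution applies: SAP 5.5 says that no PDC can be calculated after withdrawal of consent, and the number of patients with a PDC is not stated. It may be below 237. The per-protocol count of 227, with 92.4% power under the planning values, shows how much margin there is. No further enrolment is needed and no conclusion changes.

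The difference between the planning test and the van Elteren test is disclosed and is not an error.

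**What to change.** Choose one consistent statement and use it in SAP 1.2, Protocol 11.1 and the Protocol synopsis:

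- 252 patients (126 per group) at 30% dropout; or
- 248 patients at 29% dropout; or
- 248 patients at 30% dropout, leaving about 174 evaluable, with t-test power of about 84.6%.

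Recruitment is complete, so either option that keeps 248 preserves the historical target. The sponsor should pick the one that matches its calculation record. In the synopsis, replace the shorthand with the division: 176/(1 − 0.30) with 252, or the matching expression if 248 is kept. A sentence noting that 258 were randomised would settle the practical question.

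A van Elteren power is optional. If given, show it as a range with the assumed PDC distribution (about 83% if normal, higher for the bounded, skewed case examined), not as a single 83%.

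The cost is a few words in three places. Design, conduct and analysis do not change.
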